**2. Information from the Prior Approval Period**

a. Total number of subjects, samples or charts entered into study since the last IRB Initial or Continuing Review: 6

b. Have one or more subjects claimed injury from participating in this study?  
 Yes  No  N/A

c. Have any unanticipated problems, and/or adverse events related to the research occurred at this site?  
 Yes  No

d. Have any serious adverse events related to the research occurred at this site?  
 Yes  No

e. Have any participants withdrawn from this site since the last IRB review?  
 Yes  No

f. Have there been any complaints about the research at this site since the last IRB review?  
 Yes  No

g. Has there been any recent literature that may be relevant to the research since the last IRB review?  
 Yes  No

h. Have there been any relevant multi-center trial reports since the last IRB review?  
 Yes  No  N/A

i. Has there been any other relevant information, especially information about risks associated with the research (updated Investigator's Brochure, etc.) since the last IRB review?  
 Yes  No  N/A

j. Have there been any research findings since the last IRB review?  
 Yes  No

k. Has this study received any monitoring visits from the sponsor or other external compliance agencies?  
 Yes  No  
 If "YES":  
 1) How many monitoring and/or compliance visits were conducted?  
 2) Were all monitoring and/or compliance visits reported to Research Service?  Yes  No  
 3) Please provide dates and outcome of monitoring/compliance visits.

**3. Additional IRB Oversight**

Has the PI submitted this study to another IRB or IRBs?  
 Yes  No  
 • If "YES":  
 a. Provide name(s) of IRB(s): UC San Francisco Committee on Human Research (for UC Berkeley, per NOITR)  
 1) Federal Wide Assurance Number: 00000068  
 b. Status of study:  
 Under Review  Approved  Disapproved  
 • If Disapproved:  
 1) Provide details:

**B. CONFLICT OF INTEREST**

1. Describe any personal or financial interest of the investigators and research staff in the study. n/a
2. Research Financial Conflict of Interest Statement submitted for all members of the research team.  Yes  No

**D. STUDY DESIGN AND MERIT**

**1. Estimated length of study: (in years or months)**

7 years

**2. Length of each participant's time in this study: (in hours, days, weeks, months, or years)**

1 day to 9 months

**3. Purpose of study:**

**a. State the research hypothesis.**

Participation in the experimental interventions will enhance functioning in complex 'real-life' settings, result in improvements in attention and working memory (reflecting protection from distraction) and improvements on measures of sustained attention.

**b. Describe the research objectives.**

To determine the neural, neurocognitive and functional effects of attentional training protocols. We will use fMRI coupled with behavioral interventions to address the following questions: Question 1: What are the neural changes caused by brain injury that underlie behavioral changes in executive cognitive control? Question 2: What specific neural changes support improvements in cognitive abilities of executive control and attention in patients with brain injury? The studies will also investigate to what extent effects transfer to higher and lower levels of function and domains of cognitive functioning that are not explicitly trained; to what extent neural measures help to explain variability in behavioral effects; and to what extent effects are maintained at 6 months follow-up.

**c. Describe in detail the purpose of this study.**

Aim 1. To determine the neural, neurocognitive and functional effects of a theory-driven, strategy-based intervention that trains goal-oriented attention with intensive application through accomplishment of personally relevant projects. Hypothesis: Participation in the experimental intervention will enhance functioning in complex 'real-life' settings, relative to an educational intervention matched for time and attention.

Aim 2. To determine the neural, neurocognitive and functional effects of a computer-assisted game-based protocol designed to intensively train the target process of re-direction of selective attention when distracted.

Hypothesis: Participation in the experimental intervention will result in improvements in attention and working memory (reflecting protection from distraction), relative to a comparison intervention matched for time and computer usage.

Aim 3. To determine the neural, neurocognitive and functional effects of a computer-assisted training task that targets basic tonic and phasic attention functions. Hypothesis: Participation in the experimental intervention improves sustained attention, relative to a comparison intervention matched for time and computer usage.

Each study will also investigate to what extent effects transfer to higher and lower levels of function and domains of cognitive functioning that are not explicitly trained; to what extent neural measures help to explain variability in behavioral effects; and to what extent effects are maintained at 6 months follow-up.

**Describe the importance of resulting knowledge from this study.**

- d. This research is designed to contribute to improving care by (1) providing a neuroscientific framework for understanding neurorehabilitation therapies and their effects on brain functions, (2) aiding in the development of informative fMRI biomarkers that will be useful in rehabilitation treatment studies and (3) aiding in the design of novel therapeutic interventions that more directly target the underlying neural bases of dysfunction. Completion of the proposed studies will provide an essential foundation for the immediate next steps -- directly targeting the elucidated neural pathways using improved behavioral, physiological and pharmacologic modulation treatment interventions.

**4. Check types of study design:**

**Chart/Medical Records Review**

Prospective

Retrospective

**Observational (the investigator observes the events without altering them):**

Cross-sectional study (each participant examined only once)

Longitudinal study (each participant followed over a period of time)

**Experimental Intervention (the investigator observes the effect of the intervention on outcome):**

Randomized

Blinded

Retrospective

Prospective

**5. Describe statistical methods** (For example: sample size estimation, power calculation, statistical tests or descriptive statistics, data analysis tools, etc.)

Analyses of cross-sectional data will include (a) across-group comparisons using univariate statistics and (b) within group correlational analyses testing the relationships between behavioral and neural measurements. Tests of repeated measures will be used to assess the effects of the training interventions on pre- and post- intervention measurements. Intervention group x time interactions will be assessed using ANOVA and specific relationships will be tested using paired T-tests.

**6. Describe appropriateness and rationale for elements warranting special attention** (placebo, washout period, challenge study, radiation exposure, deception study, deviation from accepted standard of care).

n/a

**7. Have there been IRB approved protocol amendments modifying the study** (including sponsor amendments) since the last review?

Yes  No

- If "YES", list approval date and summarize the nature and purpose of all protocol amendments made since the time of last Initial or Continuing Review:

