\_\_Cognitive task practice: Subjects (patients and healthy volunteers) participate in cognitive task practice requiring attention and memory. These may be of short, medium and long-term duration in 3 separate stages. In the first stage, subjects may be asked to practice tasks for a single session. The short-term practice tasks involve presentations of images or words on a computer during one session lasting up to 90 minutes. In the second stage, subjects may be asked to practice tasks over 2-4 weeks. This medium-term training also involves practicing computerized cognitive tasks that involve attention and memory for 30-60 minutes a day. Subjects will be randomized into groups doing the same tasks, but in a different order. In the third stage, subjects will be asked to participate in cognitive task practice that is designed to be a form of cognitive rehabilitation training. This long-term training includes computer-assisted and therapist-guided practice 1-2 hours each day for up to 6 weeks working on cognitive tasks that engage attention, working memory, goal management and other executive functions, and may also include up to 6 weeks attending education sessions about brain health, with a therapist on an individual basis and in groups. The long-term training will include sessions with staff at the Martinez VA Outpatient Clinic, Brain Health Building and/or Center for Rehabilitation and Extended Care (CREC) on a weekly basis. Subjects in this third stage are also randomized into groups that do the same tasks, but in a different order. Assignments and materials for practicing at home will be given to patients and healthy volunteers. For computerized tasks, software for practicing tasks at home will be offered to participants. Subjects may stop participating at any time. Typically, neurocognitive testing and fMRI studies are performed before and after training.

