**b. Describe the research methods, including how the study will be implemented locally.**

The research involves (1) neurocognitive testing, (2) practice on cognitive tasks, and (3) performing MRI scans. (1) Neurocognitive testing will be done at the Martinez VA Research Building 4, Outpatient Clinic, Brain Health Building and/or Center for Rehabilitation and Extended Care (CREC); (2) practice on cognitive tasks will be done at the Martinez VA Research Building 4, Outpatient Clinic, Brain Health Building and/or Center for Rehabilitation and Extended Care or at home; and (3) performing fMRI scans will be done at the Brain Imaging Center.

**c. Provide detailed information about all study procedures, including the approximate duration and frequency of each procedure. It is not necessary to repeat descriptions of non-human related procedures from the protocol narrative (e.g. you should describe how much and how frequently blood is drawn, but not the methods for performing tests on the blood, if already stated elsewhere).**

\_\_\_ Neurocognitive measurements: This part of the experiment takes approximately 2 - 3 hours. The subject is free to take breaks throughout the session. Subjects may undergo neurocognitive measurements once if they do not undergo cognitive training, twice if they participate in short-term or medium-term training (pre- and post-training), and three times if they participate in long-term training (at baseline, 5 weeks, and 10-weeks)

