\_\_\_ Cognitive task practice: These may be of short, medium and long-term duration in 3 separate stages. In the first stage, subjects may be asked to practice tasks for a single session. The short-term practice tasks involve presentations of images or words on a computer during one session lasting up to 90 minutes. In the second stage, subjects may be asked to practice tasks over 2-4 weeks. This medium-term training also involves practicing tasks that involve attention and memory for 30-60 minutes a day. Subjects will be randomized into groups doing the same tasks, but in a different order. In the third stage, subjects may be asked to participate in cognitive task practice that is designed to be a form of cognitive rehabilitation training. This long-term training includes practicing 1-2 hours each day for up to 10 weeks working on cognitive tasks that engage attention, working memory, goal management and other executive functions, or education sessions about brain health, with a therapist on an individual basis and in groups.

\_\_\_ fMRI scanning: A session typically takes 60-90 minutes and the subject is given frequent breaks. The subject may stop the experiment at any time. Subjects may undergo fMRI once if they do not undergo cognitive training, twice if they participate in short-term or medium-term training (pre- and post-training), and three times if they participate in long-term training (at baseline, 5 weeks, and 10-weeks)

\_\_\_ EEG studies: A recording session typically takes 60-90 minutes. The subject is given breaks every 5-10 minutes, but may request a break or stop the experiment at any time. These will be done in Research Building 4 at VANCHCS Martinez.

\_\_\_ Follow-up contact: Researchers will contact subjects by telephone 6 months after other study activities to ask standardized questions about their post-participation level of functioning in various life domains. Telephone contact takes 30-60 minutes. Subjects may also be asked to return six months after their first visit for follow-up neurocognitive testing and MRI.

**d. Distinguish procedures that are for research from those that are clinically indicated and/or standard of care. All the procedures are for research.**

e. **Will any study procedures (including analysis of subject samples or data) be conducted at any site other than VANCHCS/VACCHCS?**

Yes  No

• If "YES", complete the following information:

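### The planned group-by-time ANOVA does not fix which visit tests Aim 1 in the three-visit long-term stage, and if the groups switch interventions the later visit can hide or reverse the effect

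*Combined protocol and SAP*

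**What the plan says.** Section D.5 is the only description of the analysis in this document. Repeated-measures tests are applied to "pre- and post- intervention measurements", and "Intervention group x time interactions will be assessed using ANOVA and specific relationships will be tested using paired T-tests". It gives no visit, number of time levels or Aim 1 contrast.

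Aim 1 (D.3.c) is a between-arm hypothesis: training should improve real-life functioning "relative to an educational intervention matched for time and attention".

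For neurocognitive testing and for fMRI, G.2.c schedules assessments "three times if they participate in long-term training (at baseline, 5 weeks, and 10-weeks" after enrolment in that stage. On allocation, G.2.a says "Subjects in this third stage are also randomized into groups that do the same tasks, but in a different order", and H.2.a repeats the idea. G.2.a describes "computer-assisted and therapist-guided practice 1-2 hours each day for up to 6 weeks" and adds that the stage "may also include up to 6 weeks attending education sessions about brain health". G.2.c describes "practicing 1-2 hours each day for up to 10 weeks" and joins cognitive tasks and education with an or. The interim findings (M.1) describe 22 completers randomised to active training or to brain health education, without mentioning order.

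D.3.b and D.3.c ask separately whether effects are maintained at six months.

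**The concern.** With two visits, a group-by-time interaction is a valid between-arm test of change, and the pre/post wording is enough. The short- and medium-term stages have two visits. The long-term stage has three, and there the wording admits at least three tests: baseline to week 5, baseline to week 10, and the interaction over all three visits.

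Whether these answer the Aim 1 question depends on the design. If groups receive training and education in opposite orders, both have had both by the end. A comparison made then is no longer training against education, and week 5 could be the post visit of one phase and the pre visit of the next. If the arms are parallel, both visits bear on Aim 1, but nothing says which one decides it. The paired t-tests do not fill the gap: a change within one arm cannot show an effect relative to the other.

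**Working it through.** The plan states no power, alpha, effect size, SD or correlation, so there is no figure of its own to reproduce. The numbers below are illustrations.

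**Assumed inputs.** n = 11 per arm (an even split of the 22 completers in M.1, which gives no split); outcome SD 1; equal correlation ρ = 0.4/0.6/0.8 between visits; two-sided 5%; training adds d, education adds 0; no dropout. Retention r is the share of the gain still present at week 10 in the arm trained first.

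**1. Expected between-arm difference (first-trained minus other arm).**

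| Design | Baseline | Week 5 | Week 10 |
|---|---|---|---|
| Switch between the two later visits | 0 | d | rd − d = −(1 − r)d |
| Parallel, effect sustained | 0 | d | d |

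With a switch, the week-10 difference is 0 at r = 1 and −d/2 at r = 0.5, so it is never in favour of the arm trained first.

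**2. Two-visit contrasts.** A change score has variance 2(1 − ρ). For a true difference Δ the noncentrality is Δ/√(2(1 − ρ)) × √(n/2), on 20 df.
- Δ = 1.0: 2.14/2.62/3.71, so power is 53/70/94%. This is baseline to week 5 at d = 1.0.
- Δ = 0.5 in size: 1.07/1.31/1.85, giving 17/24/42%. This is the rate of significant reversal at week 10 with a switch, d = 1.0 and half retention.
- Δ = 0.25 in size (d = 0.5, half retention): reversal in 7/9/14%.
- Δ = 0 (full retention): about 2.5% in favour of the arm trained first, which is the one-sided error rate, whatever d is.

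**3. Three-visit interaction.** Its power depends on the sum of squared deviations of the visit differences from their mean.
- Switch with full retention (0, d, 0): (1/9 + 4/9 + 1/9)d² = (2/3)d².
- Parallel (0, d, d): (4/9 + 1/9 + 1/9)d² = (2/3)d².

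The sums are equal, so a significant F cannot tell the two patterns apart. It also has no direction and, with a switch, mixes differences from before and after it.

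**4. Free choice of visit with no true effect.** Simulation with 40,000 trials per cell: at least one of the two two-visit contrasts is significant in 8.8/9.4/9.2% of trials, against 5% for one named contrast. Adding the three-visit interaction gives 9.7/10.2/10.2%. This holds under either design.

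**5. Baseline adjustment.** Relative to the change score, ANCOVA has variance (1 − ρ²)/[2(1 − ρ)] = (1 + ρ)/2 = 0.70/0.80/0.90, apart from a small loss for estimating the slope. Simulated power at d = 1.0 is 66/77/95% for ANCOVA, against 53/70/94% for the change score.

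**The case against.** Several objections are fair.

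*Group-by-time is already a between-arm test.* True. What is missing is the visits, not the comparison of arms.

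*No switch is documented.* Also true. A reader might infer a crossover at week 5 from the different-order wording and the 5- and 10-week visits, but no passage says when a switch occurs, and G.2.c and M.1 can be read as parallel arms. The reversal figures hold only if there is a switch, and they shrink at smaller d.

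*The stated durations may not conflict.* A reader might see a contradiction between up to 6 plus up to 6 weeks in G.2.a, up to 10 weeks in G.2.c, and visits at 5 and 10 weeks. All the durations are maxima, and two 5-week phases would satisfy every one of them. They need clarifying, but are not shown to contradict.

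*Six months adds no ambiguity.* Correct: the aims already make it a maintenance question.

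*The paired t-tests may only be follow-ups.* D.5 does not say they will establish the between-arm claim. One might infer from the arm-by-arm wording in M.1 that the interim conclusion rests on one arm being significant and the other not. M.1 names no test or visit, so that is not supported.

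*Details may be held elsewhere.* This is a continuing-review form, and G.2.c mentions a protocol narrative. The point is therefore about what this document states.

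**Conclusion.** The point holds, conditionally on the design. D.5 leaves the deciding visit open in the long-term stage. If the groups switch, baseline to week 10 has expected difference zero when gains last and the wrong sign when they fade; in the illustration it is significantly reversed in 17/24/42% of trials at d = 1.0 and half retention, and in 7/9/14% at d = 0.5. If the arms are parallel there is no reversal, and what remains is a false-positive rate of about 9% from choosing freely between two visits. Under either design, within-arm tests cannot support a claim relative to education.

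The sizes rest on assumed values for arm size, effect, correlation and retention. They show that the choice of visit matters. They do not show that any reported result is wrong, or that a switch took place. Confidence is medium because the design itself is unclear from this document.

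**What to change.** First, state in this document what each long-term group receives and when, relative to the 5- and 10-week visits, so that G.2.a, G.2.c, H.2.a and M.1 describe one design.

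Then make the Aim 1 test in D.5 a single contrast: the between-arm difference at the first post-intervention visit before any switch or, if the arms are parallel, at one named visit. Adjust it for the baseline value already collected (ANCOVA, or a mixed model with that contrast), include all randomised participants by assigned group, and report a 95% confidence interval. The change-score interaction on the same two visits is also valid, but less precise. Make the other visits secondary and label within-arm paired t-tests descriptive.

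The cost is wording and a rerun on data already collected. Enrolment is being closed (E.3) and no new visits are needed. Because interim results have been seen (M.1), the choice must be dated and reported as made after that look; it improves transparency but does not restore full prespecification. At 11 per arm the interval will be wide: the ANCOVA half-width is about 0.8/0.7/0.5 SD at ρ = 0.4/0.6/0.8.

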**b. How do the inclusion/exclusion criteria reflect the purpose of the study?**

The study seeks to investigate neural changes associated with clinically relevant cognitive training of patients with acquired brain injury. Variability in cognitive performance is a significant problem in the interpretation of many rehabilitation studies. Limiting the study to patients with stable, chronic deficits will facilitate the detection of changes related to the parameters of interest. Acute recovery presents a phase of high variability and ongoing neural and vascular changes, therefore only patients in chronic stages will be included. Studies at this stable phase will facilitate detection of otherwise subtle changes in these 'proof-of-principle' studies. Findings are less likely to be confounded by 'spontaneous' recovery or vascular changes.

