## M. INTERIM FINDINGS

1. **Provide a summary description of study progress, subject experiences, research results obtained thus far, and any new information since the IRB's last review.**

1. Training goal-oriented attention self-regulation amongst Veterans with chronic TBI. Twenty-two Veterans with history of chronic TBI (> 6 months) and functional complaints have completed this research protocol after having been randomized into active training (GOALS) or a comparison intervention involving brain health education (BHE). Results. GOALS participants demonstrated improvements on composite measures of attention and executive functions ( $p < 0.01$ ) and a simulated, ecologically-valid 'real world' task ( $p < 0.01$ ), as well as reported improvements on multiple aspects of cognition as it relates to daily functioning (i.e., within domains of working memory, sequencing and switching of attention, and awareness, self-monitoring, planning, task execution, learning, managing fatigue/energy, and anxiety;  $p < 0.05$ ). BHE participants did not demonstrate or report similar changes..

2. Development and preliminary testing of a cognitive training system for goal-directed self-regulation: "From Startup-to-CEO". We developed a fully manualized cognitive training system consisting of therapist-administered training and specially designed game scenarios to help illustrate, practice, and develop training concepts.

3. Preliminary data lend support to the plausibility of the hypothesized moderation and medication mechanisms under investigation in this protocol. Data also support that these approaches to training goal-oriented self-regulation are feasible and may help with transfer of skills to daily life contexts and individual goals.

**Provide a summary of any relevant recent literature since the IRB's last review.** (Attach copies of any relevant publications.)

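### The between-arm test in D.5 is a group x time ANOVA with no baseline covariate: valid, but less precise than a baseline-adjusted comparison unless the pre/post correlation is high

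*Combined protocol and SAP*

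**What the plan says.** Section D.5 is the whole of the statistical plan. On the training interventions it states: "Tests of repeated measures will be used to assess the effects of the training interventions on pre- and post- intervention measurements". The between-arm test is then named: "Intervention group x time interactions will be assessed using ANOVA and specific relationships will be tested using paired T-tests". Baseline thus enters as one of the repeated outcomes. No covariate, ANCOVA, mixed model, alpha, effect size or sample size is given there.

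Section G.2.c sets the number of assessments. In the two shorter stages, participants are measured "twice if they participate in short-term or medium-term training (pre- and post-training"). The longest stage has a fuller visit schedule, with measurement "three times if they participate in long-term training (at baseline, 5 weeks, and 10-weeks"). On the long-term stage, G.2.a adds: "Subjects in this third stage are also randomized into groups that do the same tasks, but in a different order".

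Section M reports interim results: "Twenty-two Veterans with history of chronic TBI (> 6 months) and functional complaints have completed this research protocol". Allocation in this group is described separately, as "randomized into active training (GOALS) or a comparison intervention involving brain health education (BHE"). It gives no numbers by arm.

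Section F.6.b notes that "Variability in cognitive performance is a significant problem in the interpretation of many rehabilitation studies", and answers this by restricting entry to patients with stable, chronic deficits.

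**The concern.** All three aims in section D.3.c claim an effect relative to a comparison intervention, so the between-arm estimate carries the conclusions. With a single pre/post pair, the group x time F statistic is the square of the two-sample t statistic on change scores. This forces a slope of 1 on baseline. Cognitive scores that correlate imperfectly over time regress towards the mean, so the right slope is usually below 1. Two things follow:

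- The estimate is noisier than it needs to be.
- If one arm happens to start higher, the change score subtracts too much and pushes that arm's apparent gain down.

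Section E closes enrolment with 54 entered of 210 approved (sections F.1 and F.2). More participants can no longer supply precision, which leaves the analysis as the main lever.

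**Working it through.** The documents contain no power or sample-size figure to reproduce, so this is a comparison of two analyses under stated assumptions.

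**Inputs**
- From the documents: 22 completers of the GOALS/BHE comparison (section M).
- Assumed: an 11:11 split, equal pre and post SDs (set to 1), an effect of 0.8 SD, two-sided 0.05, and r from 0.4 to 0.9.

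**Variance**
- Change score, per participant: 2(1 - r).
- ANCOVA, per participant: 1 - r².
- Large-sample ratio ANCOVA/change: (1 - r²) / [2(1 - r)] = (1 + r)/2.
- Cost of estimating the slope at N = 22: 1 + 1/(N - 4) = 19/18 = 1.056, with 19 rather than 20 degrees of freedom.
- Net ratio: (1 + r)/2 × 1.056.

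**Worked case, r = 0.5**
- Change-score SE = √(2 × 0.5 × 2/11) = 0.426. 0.8/0.426 = 1.88 on 20 df gives 43% power (noncentral t).
- ANCOVA SE = √(0.75 × 2/11 × 1.056) = 0.379. 0.8/0.379 = 2.11 on 19 df gives 52% power.

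| r | Net variance ratio | Power, change score | Power, ANCOVA |
|---|---|---|---|
| 0.4 | 0.74 | 37% | 47% |
| 0.5 | 0.79 | 43% | 52% |
| 0.6 | 0.84 | 51% | 58% |
| 0.7 | 0.90 | 64% | 68% |
| 0.8 | 0.95 | 81% | 82% |
| 0.9 | 1.00 | 98% | 98% |

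**Break-even.** Setting (1 + r)/2 × 19/18 = 1 gives r = 17/19 = 0.895. Above that, ANCOVA gains nothing at this size.

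**Baseline imbalance.** Let d be the baseline difference between arms. Given d, the expected post-training difference is effect + r·d. Subtracting d leaves effect - (1 - r)·d. At 11 per arm, d has SD √(2/11) = 0.43 and exceeds 0.5 SD in either direction in about 24% of randomisations. For d = 0.5 SD, the change-score estimate is off by -0.25 SD at r = 0.5, -0.15 at r = 0.7 and -0.05 at r = 0.9.

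**Simulation.** With 40,000 trials per case at 11:11, the variance ratios were 0.787, 0.897 and 1.003 at r = 0.5, 0.7 and 0.9. Both estimators averaged about 0.8, and type I error was about 5% for both. The slope of the estimate on d was -0.5, -0.3 and -0.1 for change scores and about 0 for ANCOVA. Splits of 12:10 and 14:8 gave almost the same variance ratios.

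**Long-term stage.** With two groups and three visits, the omnibus interaction has (2 - 1)(3 - 1) = 2 df, so it is not a single change-score test. If the groups receive the same components in a different order, both may have had both by week 10. The omnibus test then mixes the first-period contrast with what follows. The identity with a change-score test is exact only for a chosen pair of visits, such as baseline and 5 weeks.

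**The case against.** The strongest reply is that the planned test is a standard, valid analysis, and that this is a choice of efficiency between two accepted methods. That stands, and it limits the grade of the point. Several stronger readings are tempting, and the documents do not support them:

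- **That the planned test is biased or ignores baseline.** It subtracts baseline in full. The residual error is over-correction, conditional on the imbalance that occurs. It is not average bias or type I inflation.
- **That ANCOVA always wins.** At 22 participants it does not above r of about 0.895, and at 0.7 to 0.8 the gain is small.
- **That this is a trial of 11 per arm.** Section M gives 22 completers of one comparison at an interim point, without a split. The final analysed number is not stated. Even if all 54 people ever entered formed one two-arm comparison (27 per arm, an upper bound that the documents do not support), power for 0.5 SD would still go from 44% to 54% at r = 0.5.
- **That variability is the trial's main interpretive problem.** F.6.b calls it significant in many studies, and its remedy is eligibility.
- **That every randomised participant has a baseline on every measure.** G.2.a says only that testing and scanning before and after training are typical, and F.6.a excludes some patients from MRI alone.

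It is also fair that D.5 is a short field in a continuing-review form, so the absence of adjustment is read from its silence. But D.5 does name a test, and that test has no covariate. Finally, results by arm are already reported, so a change now is a late one and must be disclosed.

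**Conclusion.** The point holds as a matter of precision and not of validity. D.5 names an unadjusted group x time ANOVA, although the design provides for baseline measurement. Under the assumptions above, the gain from adjustment is about 7 to 10 percentage points of power at r = 0.4 to 0.6, 1 to 5 points at 0.7 to 0.8, and nothing from about 0.9. The size rests on r, the arm split and the effect, none of which the documents give. A reader might go on to infer that the interim GOALS findings are artefacts of the test. Nothing here supports that, since the test keeps its error rate. A reader might also take any baseline-adjusted arm difference as the training effect. In the order-randomised long-term stage that does not follow at week 10. The change is worth making because it is almost free.

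**What to change.** In D.5, make the between-arm test a regression of the post-training score on randomised group and the baseline score of the same measure. Report the adjusted mean difference with its 95% CI. Apply it to each measure for participants who have a baseline value on it.

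For long-term training, apply it to the 5-week between-arm contrast, before the groups change over. D.5 should say explicitly that the changeover follows that visit: the documents imply this through the visit schedule and the order randomisation but do not state it. The 10-week arm difference and the 2-df omnibus interaction should not be read as the training effect.

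Because section M already reports results by arm, date and document the change, and keep the group x time ANOVA as a sensitivity analysis.

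The cost is a few sentences, one degree of freedom, no gain if r is about 0.9 or higher, and disclosure of a late change. No new data are needed.
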